Clinical Study Protocol Drug Substance AZD8931 Study Code D0102C00007 Edition Number 1.0 Date

[¹⁴C] AZD8931 – A Phase I, Open Label Study of the Absorption, Metabolism, Excretion, and Pharmacokinetics Following a Single Oral Dose to Healthy Male Subjects

Sponsor: AstraZeneca AB, [name]

The following Amendment(s) and Administrative Changes have been made to this protocol since the date of preparation:

Amendment No.	Date of Amendment	Local Amendment No:	Date of Local Amendment
Administrative Change No.	Date of Administrative Change	Local Administrative Change No.	Date of Local Administrative Change

This submission /document contains trade secrets and confidential commercial information, disclosure of which is prohibited without providing advance notice to AstraZeneca and opportunity to object.

[¹⁴C] AZD8931 – A Phase I, Open Label Study of the Absorption, Metabolism, Excretion, and Pharmacokinetics Following a Single Oral Dose to Healthy Male Subjects

Principal Investigator

Study centre and number of subjects planned

The study will be performed at a single study centre in 6 healthy male subjects.

Study period	Phase of development
Estimated date of first subject enrolled	Clinical pharmacology
Estimated date of last subject completed	

Objectives

Primary objective

To characterise the absorption, metabolism, excretion, and pharmacokinetics of a single oral dose of 160 mg $[^{14}C]$ AZD8931 in healthy male subjects.

Secondary objective

To further determine the safety and tolerability of a single oral dose of 160 mg $[^{14}C]$ AZD8931 in healthy male subjects.

Exploratory objectives

1. Collect optional blood samples for DNA extraction and storage to enable an investigation into the impact of polymorphisms on the absorption, distribution,

Clinical Study Protocol Synopsis Drug Substance AZD8931 Study Code D0102C00007 Edition Number 1.0 Date

metabolism, and excretion-related genes, eg, the effect of cytochrome P450 2D6 genotype on AZD8931 pharmacokinetics (the data will be reported separately)

2. Perform possible exploratory analysis of significant metabolites in plasma, urine, and faecal samples (the data will be reported separately)

Study design

This is an open label, single dose study of the excretion of radioactivity, absorption, metabolism, pharmacokinetics, safety, and tolerability following a single oral dose of [¹⁴C] AZD8931 conducted at a single study centre in 6 healthy male subjects.

Target subject population

Healthy male subjects, aged 50 to 65 years (inclusive) with regular daily bowel movements

Investigational product, dosage and mode of administration

Each subject will receive a single oral dose of 160 mg [¹⁴C]-labelled AZD8931, containing 7.4 MBq (200 μ Ci) administered as an oral solution.

Comparator, dosage and mode of administration

None

Duration of treatment

A single dose of AZD8931 will be administered. The study will consist of 3 visits. Visit 1, Screening will take place within 28 days before Visit 2, Day 1. Visit 2 will be the residential period when each subject will be resident in the study centre for 11 days from Day -1 until Day 11 (240 hours postdose). Visit 3, Follow-up will occur 5 to 10 days after the last sample has been collected.

Outcome variable(s):

• Pharmacokinetics

AZD8931 and o-desmethyl AZD8931 (AZD8931 metabolite) whole blood and plasma concentrations will be used to assess the following parameters, as applicable:

Area under the plasma concentration-time curve from zero to infinity (AUC); area under the plasma concentration-time curve from zero to the time of the last quantifiable radioactivity or concentration (AUC_(0-t)); area under the plasma concentration-time curve from zero to 12 hours (AUC₍₀₋₁₂₎); area under the plasma concentration-time curve from zero to 24 hours (AUC₍₀₋₂₄₎); maximum plasma concentration (C_{max}); time to maximum plasma concentration (t_{max}); terminal half-life (t_{½λz}); apparent plasma clearance (CL/F); apparent volume of distribution during terminal phase (V_z/F); volume of distribution at steady state (V_{ss}/F); metabolite to parent ratio of AUC (MR_{AUC}); and metabolite to parent ratio of C_{max} (MR_{Cmax}).

Whole blood, plasma, urine, and faeces radioactivity data will be used to assess the following parameters, as applicable:

AUC from whole blood and plasma radioactivity-time curvel; amount of radioactivity excreted in urine (Ae_u); amount of radioactivity excreted in faeces (Ae_f); amount of radioactivity excreted in urine and faeces (Ae_{u+f}); radioactivity excreted in faeces as a percentage of dose (fe_u); radioactivity excreted in faeces as a percentage of dose (fe_f); and radioactivity excreted in urine and faeces as a percentage of dose (fe_{u+f}).

The ratio of plasma AZD8931 concentration versus plasma radioactivity, the ratio of plasma o-desmethyl AZD8931 concentration versus plasma radioactivity, and the ratio of whole blood radioactivity versus plasma radioactivity will be calculated at each time point for each subject.

The ratio of plasma AZD8931 AUC versus plasma radioactivity AUC, the ratio of plasma o-desmethyl AZD8931 AUC versus plasma radioactivity AUC, and the ratio of whole blood radioactivity AUC versus plasma radioactivity AUC will be calculated for each subject.

• Safety

Adverse events, physical examinations, ophthalmology assessments, vital signs, electrocardiograms, and clinical laboratory assessments.

Statistical methods

No formal statistical hypothesis testing will be performed in this study. All data collected and parameters derived for the study population, sample size, pharmacokinetics, and safety will be summarized descriptively.

Pharmacokinetic radioactivity and concentration data as well as derived pharmacokinetic parameter data will be summarized by matrix (blood, plasma, urine, and faeces) and analyte (radioactivity, AZD8931, and o-desmethyl AZD8931) using descriptive statistics and graphically displayed as appropriate.

Adverse events will be collected from the time of signing informed consent throughout the treatment period and including the follow-up period. All adverse event data will be listed for all subjects. The number of adverse events experienced following dosing will be summarized in tables using Medical Dictionary for Regulatory Activities system of nomenclature by system organ class and preferred term; with preferred term sorted according to associated total subject incidence (in descending order). These summary tables will also be produced with severity of adverse event added as an additional classification factor. Similarly, the number of

serious adverse events, other significant adverse events, adverse events that led to discontinuation, and treatment related adverse events will be summarized.

Additional post-hoc summary and/or analysis may be performed as appropriate.

TABLE OF CONTENTS

PAGE

	TITLE PAGE	1
	PROTOCOL SYNOPSIS	2
	TABLE OF CONTENTS	6
	LIST OF ABBREVIATIONS AND DEFINITION OF TERMS	10
1.	INTRODUCTION	12
1.1	Background	12
1.2	Research hypothesis (Not applicable)	14
1.3	Rationale for conducting this study	14
1.4	Benefit/risk and ethical assessment	14
2.	STUDY OBJECTIVES	15
2.1	Primary objective	15
2.2	Secondary objective	15

11.2	Calculation or derivation of pharmacokinetic variables	46
12.	STATISTICAL METHODS AND SAMPLE SIZE DETERMINATION.	48
12.1 12.1.1 12.1.2 12.1.3	Description of analysis sets Safety analysis set Pharmacokinetic analysis set Interim pharmacokinetic analysis	
12.2	Methods of statistical analyses	
12.2.1	Subject characteristics	49
12.2.2 12.2.3	Safety and tolerability Pharmacokinetics	
12.2.4	Interim analyses	
12.3	Determination of sample size	51
12.4	Data monitoring committee	51
13.	IMPORTANT MEDICAL PROCEDURES TO BE FOLLOWED BY TH INVESTIGATOR	
13.1	Medical emergencies and AstraZeneca contacts	
13.2	Overdose	
13.3	Pregnancy	
13.3.1	Maternal exposure	53
13.3.2	Paternal exposure	
14.	LIST OF REFERENCES	54

LIST OF TABLES

Table 1	Study assessments	17
Table 2	Laboratory safety variables	33
Table 3	Volume of blood to be drawn from each subject	36

LIST OF FIGURES

Figure 1	Study flow chart16
----------	--------------------

LIST OF APPENDICES

Appendix A	Signatures
Appendix B	Additional Safety Information
Appendix C	International Airline Transportation Association (IATA) 6.2 Guidance Document

LIST OF ABBREVIATIONS AND DEFINITION OF TERMS

The following abbreviations and special terms are used in this study Clinical Study Protocol.

Abbreviation or special term	Explanation
λ_z	Terminal elimination rate constant
%AUCex	Percentage of AUC obtained by extrapolation
ADME	Absorption, distribution, metabolism, and excretion
ADR	Adverse drug reaction
AE	Adverse event (see definition in Section $6.3.1$)
Ae _f	Amount of radioactivity excreted in faeces
Ae _u	Amount of radioactivity excreted in urine
Ae_{u+f}	Amount of radioactivity excreted in urine and faeces
ARSAC	Administration of Radioactive Substances Advisory Committee
ATP	Adenosine triphosphate
AUC	Area under the concentration- or radioactivity-time curve from zero to infinity
AUC _(0-t)	Area under the concentration-time curve from zero to the time of last quantifiable concentration or radioactivity
AUC(0-12)	Area under the concentration-time curve from zero to 12 hours
AUC(0-24)	Area under the concentration-time curve from zero to 24 hours
BMI	Body mass index
CL/F	Apparent plasma clearance
C _{max}	Maximum concentration
CRF	Case Report Form (electronic)
CTCAE	Common Terminology Criteria for Adverse Events
CV	Coefficient of variance
СҮР	Cytochrome P450
EC	Ethics Committee, synonymous to Institutional Review Board (IRB) and Independent Ethics Committee (IEC)
ECG	Electrocardiogram
EDC	Electronic Data Capture
EGFR	Epidermal growth factor receptor
fe _f	Radioactivity excreted in faeces as percentage of dose

Clinical Study Protocol Drug Substance AZD8931 Study Code D0102C00007 Edition Number 1.0 Date

Abbreviation or	Explanation
special term	-
fe _u	Radioactivity excreted in urine as percentage of dose
fe_{u+f}	Radioactivity excreted in urine and faeces as percentage of dose
GCV	Geometric mean CV
HER	Human epidermal growth factor receptor
HIV	Human immunodeficiency virus
ICRP	International Commission on Radiological Protection
LIMS	Laboratory Information Management System
LLOQ	Lower limit of quantitation
MAD	Multiple ascending dose
MedDRA	Medical Dictionary for Regulatory Activities
MR _{AUC}	Metabolite to parent ratio of AUC
MR _{Cmax}	Metabolite to parent ratio of C _{max}
NA	Not applicable
NQ	Not quantifiable
OAE	Other significant adverse event (see definition in Section 11.1.1)
PD	Pharmacodynamic(s)
PK	Pharmacokinetic(s)
Rsq	Coefficient of determination
SAD	Single ascending dose
SAE	Serious adverse event (see definition in Section 6.3.2).
SD	Standard deviation
SUSAR	Suspected unexpected serious adverse reaction
$t_{\nu_{2\lambda Z}}$	Terminal half-life
t _{max}	Time to maximum concentration
UVA	Ultraviolet light wavelength A
UVB	Ultraviolet light wavelength B
V _{ss} /F	Volume of distribution at steady state
V _z /F	Apparent volume of distribution during terminal phase
WHO	World Health Organisation

Clinical Study Protocol Drug Substance AZD8931 Study Code D0102C00007 Edition Number 1.0 Date

1. INTRODUCTION

1.1 Background

AZD8931 is an oral, equipotent inhibitor against epidermal growth factor receptor (EGFR), erbB2 and erbB3, in development for the treatment of solid tumours.

The EGFR family includes 4 members; EGFR/erbB1, erbB2/human epidermal growth factor receptor (HER) 2, erbB3/HER3, and erbB4/HER4, and has been identified as a promising target for anti-cancer therapy. Ligand binding to the EGFR, erbB3, and erbB4 receptors induces receptor homo- and hetero-dimerisation, leading to phosphorylation of critical sites in the tyrosine kinase domain, and subsequent activation of downstream pathways involved in cellular proliferation and survival (Olayioye et al 2000). The preferred dimerisation partner for the other family members is erbB2. Even though it has no ligand it does become activated following dimerisation and erbB2-containing dimers exert the most potent mitogenic signal (Graus Porta et al 1997).

Aberrant EGFR and erbB2 activity have been identified in a number of human malignancies and are notable for their association with a more aggressive disease course and poor clinical outcome (Sjogren et al 1998; Nicholson et al 2001). In human tumours, activation occurs through receptor over-expression, autocrine growth factor loops, or the presence of activating mutations in the kinase domain (Voldborg et al 1997).

Epidermal growth factor receptor activation is seen in tumour types such as non-small cell lung cancer, breast, colorectal, and head and neck cancer. Over-expression of erbB2 is seen in a proportion of breast, ovarian, bladder, and gastric malignancies. Recent data suggest that simultaneous inhibition of EGFR, erbB2, and erbB3 may be of particular value in certain segments of breast cancer.

AZD8931 is being developed as a selective, oral, adenosine triphosphate (ATP)-competitive inhibitor of both EGFR and erbB2 receptor tyrosine kinases, with the expectation that it will provide superior efficacy compared to currently available inhibitors of either target alone. Nonclinical in vitro and in vivo assays have demonstrated activity against both receptor tyrosine kinases in enzyme assays, cell receptor phosphorylation, cell proliferation and survival, in in vivo pharmacodynamic (PD) assays, and xenograft tumour growth models.

A series of safety pharmacology and genetic toxicology studies, in addition to toxicology studies in rats and dogs, have been conducted with AZD8931.

AZD8931 was not genotoxic in either in vitro or in vivo assays.

On repeat administration of AZD8931 in rats, gastrointestinal toxicity was dose limiting. Epithelial degeneration and atrophy, consistent with the pharmacology of the compound, was evident on histopathological examination of a number of tissues including the skin and gastrointestinal and genitourinary tracts. There was evidence of reversibility following a 4-week recovery period.

In dogs, repeat administration of AZD8931 was associated with epithelial degeneration and atrophy in the cornea, skin, gastrointestinal tract, and genitourinary tract. These findings are consistent with the pharmacology of AZD8931 and there was evidence of reversibility of findings following a 4-week recovery period.

Dose limiting toxicity on repeat administration in the dog was corneal epithelial ulceration and in the 1-month study resulted in the termination of one high dose animal following 7 days of dosing due to a severe ulceration. In surviving animals recovery of less severe corneal ulceration was observed in life, despite continued dosing. In a single ascending dose (SAD) study in the dog, corneal translucency was observed in life but a mild corneal epithelial ulceration was seen on histopathology. Gastrointestinal toxicity was dose limiting in the SAD study.

In vitro assays indicate a potential for QT-prolongation and arrhythmia with AZD8931. There was no evidence of QT-prolongation in the in vivo cardiovascular studies. Intravenous administration of AZD8931 in an anaesthetised dog model at a dose of 30 mg/kg resulted in hyperkalaemia with associated electrocardiogram (ECG) waveform changes. Hyperkalaemia was not seen following oral dosing to conscious dogs. Reductions in arterial blood pressure were also observed at this dose level in anaesthetised dogs. In a dog SAD study, at doses of 7.1 mg/kg and above, AZD8931 produced reversible reductions in arterial blood pressure.

Dose related increases in plasma glucose, generally accompanied by increases in plasma cortisol have been observed in dogs following oral administration of AZD8931. Hyperglycaemia had reversed by 24 hours. The insulin response to hyperglycaemia appeared to be attenuated at high plasma levels of AZD8931.

A potential photo toxicity risk with AZD8931 has been identified based on the light absorption profile of the compound and a positive result in the fibroblast 3T3 cell assay.

To date the AZD8931 AstraZeneca clinical development programme comprises a completed Phase I SAD study in healthy subjects (Study D0102C00001), a completed Phase I food effect study in healthy subjects (Study D0102C00011), an ongoing Phase I multiple ascending dose (MAD) study in patients with advanced cancer (Study D0102C00002), an ongoing Phase I dose escalation study in Japanese patients with advanced solid tumours (monotherapy) or advanced breast cancer (in combination with paclitaxel) (Study D0102C00010), and an ongoing Phase I/II study in combination with paclitaxel comprising a dose escalation component (in patients with advanced solid malignancies) and a randomised, double-blind component (in patients with breast cancer) (Study D0102C00003). As of 01 November 2010, 111 subjects (64 healthy subjects and approximately 12048 patients with advanced cancer [mostly patients with advanced breast cancer]) have received single or multiple oral doses of AZD8931 twice daily either as monotherapy or in combination with paclitaxel chemotherapy or anastrozole endocrine therapy in AstraZeneca-sponsored studies. AstraZeneca will immediately notify the Principal Investigator if any additional safety information becomes available during the study.

Further information on the investigational product can be found in the Investigator's Brochure.

1.2 Research hypothesis (Not applicable)

1.3 Rationale for conducting this study

There is presently little in vivo data on the metabolic conversion of AZD8931 in man, or the routes and rates of excretion of AZD8931 or any metabolites. This mass balance study will provide definitive information about the metabolic fate, excretion, and pharmacokinetics (PK) of [¹⁴C] AZD8931 and the resultant data will be used to establish the degree of similarity between the metabolism of AZD8931 in humans and the various species used during the toxicity evaluation.

1.4 Benefit/risk and ethical assessment

The potential for adverse drug reactions (ADRs) associated with AZD8931 are based on the adverse event (AE) profile of the class of drugs that inhibit the EGFR and/or erbB2 signalling pathways, and from observations from nonclinical and clinical studies of AZD8931. Specific subject selection criteria and appropriate safety assessments have been incorporated into the clinical programme for AZD8931 based on the potential adverse effects and ADR profile.

The tolerability and initial PK of AZD8931 monotherapy was investigated in a Phase I study (Study D0102C00001) in 40 healthy male subjects. On the basis of all safety data, AZD8931 has shown a favourable safety profile, being tolerated as single oral doses ranging from 2.5 to 200 mg in healthy subjects. Rash/acne type events were reported, consistent with the known safety profile of the erbB1 tyrosine kinase inhibitor class. No subjects experienced clinically relevant changes in safety parameters such as physical examinations (including ophthalmologic assessments), blood pressure, pulse, ECG parameters, urinalysis, clinical chemistry, or haematological assessments. Asymptomatic corneal epithelial changes, detected by fluorescence staining, were noted in 1/5 of the healthy subjects treated with 200 mg in the study. These findings were suggestive of superficial desquamation, and an external ophthalmology expert confirmed that normal environmental factors (eg. swimming in chlorinated water) could result in similar observations. These findings were seen on Day 5 only and began resolving within a few hours after being noticed. Complete resolution was documented 3 days later. The external ophthalmologist providing corneal evaluation expertise to the AZD8931 clinical studies has deemed these findings as highly unlikely to be drug related. Based upon the comprehensive review of the safety data, PK data and statistical analyses of ECGs, it was concluded that no changes in QTc of any clinical concern were seen at the exposures reached in this study.

The effect of food on the PK of AZD8931 was investigated in 24 healthy subjects receiving a single dose of 160 mg AZD8931 in a 3-period cross-over study (Study D0102C00011). No deaths or serious adverse events (SAEs) were reported in this food-effect study. Adverse

events were reported for 21 of the 24 healthy subjects (88%) participating in the study. Skin-type AEs were reported by 75% of the subjects. Skin-type AEs, excluding application site reactions, were reported by 67% of the subjects. All of the skin-type AEs were considered to be mild (Common Terminology Criteria for Adverse Events [CTCAE] grade 1), except for the macular rash (CTCAE grade 2) reported by the subject who was discontinued from the study. There were no clinically relevant changes in potassium, glucose, other safety laboratory variables, vital signs, ECG, or physical examination.

For this current study subjects will be instructed to use sunscreen (with a sun factor of >30) for up to 3 months after administration of the investigational product due to the phototoxicity risk. Baseline and postdose ophthalmology assessments, and ad hoc AE-triggered assessments will be performed to monitor ocular surface and vision effects.

Further information regarding the benefit/risk profile can be found in the Investigator's Brochure.

2. STUDY OBJECTIVES

2.1 **Primary objective**

To characterise the absorption, metabolism, excretion, and PK of a single oral dose of 160 mg $[^{14}C]$ AZD8931 in healthy male subjects.

2.2 Secondary objective

To further determine the safety and tolerability of a single oral dose of 160 mg $[^{14}C]$ AZD8931 in healthy male subjects.

2.3 Exploratory objectives

- 1. Collect optional blood samples for DNA extraction and storage to enable an investigation into the impact of polymorphisms on the absorption, distribution, metabolism, and excretion (ADME)-related genes, eg, the effect of cytochrome P450 (CYP) 2D6 genotype on AZD8931 PK (the data will be reported separately)
- 2. Perform possible exploratory analysis of significant metabolites in plasma, urine, and faecal samples (the data will be reported separately)

3. STUDY PLAN AND PROCEDURES

This Clinical Study Protocol has been subject to a peer review according to AstraZeneca standard procedures.

3.1 Overall study design and flow chart

This is an open label, single dose study conducted at a single study centre in 6 healthy male subjects. All subjects will receive a single dose of $[^{14}C]$ AZD8931 on Day 1.

The study will consist of 3 visits. Visit 1, Screening will take place within 28 days before Visit 2, Day 1. Visit 2 will be the residential period when each subject will be resident in the study centre for 11 days from Day -1 until Day 11 (240 hours postdose). Visit 3, Follow-up will occur 5 to 10 days after the last sample has been collected.

The study flow chart is presented in Figure 1 and the study assessments in Table 1.

Figure 1 Study flow chart

[figure not shown]

Table 1Study assessments

Visit	Visit 1 (screening)		sit 2 ial period)	Visit 3 (Follow-up)
Day	≤28 days before Visit 2	Day -1	Days 1-11	5-10 days after last sample collection
Inclusion/exclusion criteria	Х			
Informed consent	Х			
Demographic data	Х			
Medical history	Х			
Drugs of abuse and alcohol urine screen	X°	Х		
Serology for hepatitis and HIV	Х			
Height and weight measurements	Х			X^n
Admission to study centre		Х		
Dosing			\mathbf{X}^{f}	
Discharge from study centre			X^{g}	
Adverse event recording	Х	Х	Х	Х
Concomitant medications	Х	Х	Х	
Vital signs ^a	Х		X^h	Х
12-Lead electrocardiogram	Х		X^h	Х
Safety clinical laboratory evaluations	Х	Х	X^{i}	Х
Physical examination	Х			Х
Ophthalmology	Х			Х
Blood sample for pharmacogenetics (optional)	X ^e			
Blood sampling for total radioactivity count and AZD8931 and its metabolite (if feasible) concentration ^b			$\mathbf{X}^{\mathbf{j}}$	
Blood sampling for metabolite profiling			X^k	
Urine sampling for total radioactivity count and metabolite profiling ^c			X^l	
Faeces sampling for total radioactivity count and metabolite profiling ^{c,d}			X^m	

^a Supine blood pressure and pulse.

^b Additional collections of blood samples (5.7 mL) at 24-hour intervals may cease if no radioactivity is detected in 2 consecutive plasma samples.

^c Additional 24-hour collection of urine and/or faeces may continue until 90% total recovery is achieved or recovery in urine/faeces in the 24-hour period is less than 1% of the total administered dose of radioactivity.

Clinical Study Protocol Drug Substance AZD8931 Study Code D0102C00007 Edition Number 1.0 Date

- ^d Toilet paper (first 2 wipes) collected for the first 48 hours postdose.
- ^e Timing of sample collection at the discretion of the study centre.
- f Day 1 (0 hours).
- ^g Day 11 (after the 240 hours postdose sample has been collected).
- ^h Predose, 24 hours postdose, and Day 11.
- ⁱ 24 hours postdose, and Day 11.
- ^j Predose, 1, 2, 4, 6, 8, 12, 24, 48, 72, 96, 120, 144, 168, 192, 216, and 240 hours postdose.
- ^k 1, 4, 6, 12, and 24 hours postdose.
- ¹ Predose (-12 to 0 hours), 0 to 6, 6 to 12, 12 to 24, 24 to 48, 48 to 72, 72 to 96, 96 to 120, 120 to 144, 144 to 168, 168 to 192, 192 to 216, and 216 to 240 hours postdose.
- ^m Predose (-48 to 0 hours), 0 to 24, 24 to 48, 48 to 72, 72 to 96, 96 to 120, 120 to 144, 144 to 168, 168 to 192, 192 to 216, and 216 to 240 hours postdose.
- ⁿ Weight only.
- ^o Drugs of abuse only.
- HIV: human immunodeficiency virus

If a subject vomits within 2 hours of dosing, the vomit should be retained for radioactivity analysis.

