11.2 Calculation or derivation of pharmacokinetic variables

The PK analyses of the plasma concentration data for AZD8931 and o-desmethyl AZD8931, as well as the radioactivity data for whole blood, plasma, urine, and faeces, will be performed at . Pharmacokinetic analyses will be conducted according to Standard Operating Procedures and Work Instructions for PK analyses if not otherwise specified.

Pharmacokinetic parameters will be derived using noncompartmental method with WinNonlin Professional Version 5.2 or higher (Pharsight Corp., Mountain View, California, United States of America) or SAS[®] Version 9.1 or higher (SAS Institute, Inc., Cary, North Carolina, United States of America). The actual sampling times will be used in the PK parameter calculations. Nominal times will be used for any interim PK analyses.

The following PK parameters will be derived from AZD8931 and o-desmethyl AZD8931 (if feasible) whole blood and plasma concentration data:

- Area under the concentration-time curve from zero to infinity (AUC)
- Area under the concentration-time curve from zero to the time of the last quantifiable concentration or radioactivity $(AUC_{(0-t)})$
- Area under the concentration-time curve from zero to 12 hours $(AUC_{(0-12)})$
- Area under the concentration-time curve from zero to 24 hours $(AUC_{(0-24)})$
- Maximum concentration (C_{max})
- Time to maximum concentration (t_{max})

- Terminal half-life $(t_{\frac{1}{2}\lambda z})$
- Apparent plasma clearance (CL/F), for AZD8931 only
- Apparent volume of distribution during terminal phase (V_z/F) , for AZD8931 only
- Volume of distribution at steady state (V_{ss}/F), for AZD8931 only
- Metabolite to parent ratio of AUC (MR_{AUC}) for AZD8931 and o-desmethyl AZD8931 only
- Metabolite to parent ratio of C_{max} (MR_{Cmax}) for AZD8931 and o-desmethyl AZD8931 only

The following PK parameters will be calculated for diagnostic purposes and listed, but will not be summarised:

- Terminal elimination rate constant (λ_z). Lambda z and related parameters will be reported only if coefficient of determination (Rsq) is greater than or equal to 0.80
- The time interval (h) of the log-linear regression used to determine $t_{\frac{1}{2}\lambda z}$
- Number of data points included in the log-linear regression analysis
- Rsq for calculation of λ_z
- Percentage of AUC obtained by extrapolation (%AUCex). If the %AUCex is greater than 30%, then AUC will not be reported

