Any anomalous concentration values observed at the predose time point shall be identified in the PK analysis review documentation with a description of how the value was treated for the computation.

If an anomalous concentration value is observed at the terminal phase and is judged as physiologically unreasonable, it will be excluded from computing PK parameter estimates.

The following PK parameters will be calculated from AZD8931 and o-desmethyl AZD8931 (if feasible) whole blood, plasma, urine, and faeces radioactivity data:

- Area under the whole blood and plasma radioactivity-time curve (AUC)
- Amount of radioactivity excreted in urine (Ae_u)
- Amount of radioactivity excreted in faeces (Ae_f)
- Amount of radioactivity excreted in urine and faeces (Ae_{u+f})

- Radioactivity excreted in urine as a percentage of dose (fe_u)
- Radioactivity excreted in faeces as a percentage of dose (fe_f)
- Radioactivity excreted in urine and faeces as a percentage of dose (fe_{u+f})

The ratio of plasma AZD8931 AUC versus plasma radioactivity AUC, the ratio of plasma o-desmethyl AZD8931 AUC versus plasma radioactivity AUC, and the ratio of whole blood radioactivity AUC versus plasma radioactivity AUC will be calculated for each subject.

Additional PK parameters will be determined if deemed appropriate.

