12.1.2 Pharmacokinetic analysis set

The PK analysis set will include all healthy subjects who took at least one dose of AZD8931 and have at least one postdose PK measurement without important protocol deviations or violations thought to significantly affect the PK of the investigational product. Data from healthy subjects with deviations determined to affect PK will be excluded from the PK analysis set. A strategy for dealing with data affected by protocol violations and deviations will be agreed by the study team physician, pharmacokineticist, and statistician, prior to clean file and code break.

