12.2.3 Pharmacokinetics

A listing of PK blood sample collection times as well as derived sampling time deviations will be provided. A listing of urine and faeces sample collection start and stop times will be provided. A subject listing of all whole blood, plasma, urine, and faeces radioactivity-time data, as well as plasma AZD8931 and o-desmethyl AZD8931 concentration-time data will be presented.

Pharmacokinetic variables will be summarized by matrix (blood, plasma, urine, and faeces) and analyte (AZD8931, o-desmethyl AZD8931, and radioactivity) using appropriate descriptive statistics (eg, n, arithmetic mean, SD, and coefficient of variance [CV] %, geometric mean, and geometric CV [GCV], minimum, median, and maximum). The geometric mean is calculated as the exponential of the arithmetic mean calculated from data on a log scale. The GCV is calculated as $100\% \cdot \sqrt{(\exp(s^2)-1)}$ where s is the SD of the data on a log scale. Graphical presentations of PK variables will be used as appropriate.

The ratio of plasma AZD8931 concentration versus plasma radioactivity, the ratio of plasma o-desmethyl AZD8931 concentration versus plasma radioactivity, and the ratio of whole blood radioactivity versus plasma radioactivity will be calculated at each time point for each subject.

Plasma concentrations below the lower limit of quantitation (LLOQ) will be handled as follows:

- At a time point where at least one value is above LLOQ but less than or equal to 50% values below LLOQ, all values below LLOQ are set to LLOQ and a mean (arithmetic and geometric) value and SD and CV (%) are calculated
- At a time point where more than half of the observations are below LLOQ only individual values are reported; mean, SD, geometric mean, and CV (%) will be set to not quantifiable (NQ). The minimum value and the median are set to less than LLOQ
- If all values are below LLOQ at any time point no descriptive statistics are calculated for that time point. Write not applicable (NA) in the field for SD and CV (%) and write less than LLOQ in fields for mean, geometric mean, minimum, median, and maximum in the table
- The number of observations greater than LLOQ (number of observations above LLOQ [N>LLOQ]) will be reported in the table

Figures of geometric mean radioactivity-time and concentration-time data will be presented on linear and semi-logarithmic scales by dosing regimen. Individual subject radioactivity-time

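### Vomit is kept only for the first 2 hours after dosing and has no place in the recovery variables, so the mass balance cannot be closed if a subject vomits later

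*Protocol*

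**What the plan says.** The only instruction on vomit stands below Table 1 in Protocol Section 3.1: "If a subject vomits within 2 hours of dosing, the vomit should be retained for radioactivity analysis". Nothing is said about vomit after 2 hours, or about how the measured radioactivity is to be used.

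The Synopsis and Section 11.2 define recovery as the amount of radioactivity in urine, in faeces and in the two together, and each of these as a percentage of dose. Section 12.2.3 adds: "Pharmacokinetic variables will be summarized by matrix (blood, plasma, urine, and faeces) and analyte". Its data listing names the same four matrices, as does the radioactivity laboratory's scope in Section 6.4.2. Table 1 note c reads: "Additional 24-hour collection of urine and/or faeces may continue until 90% total recovery is achieved", with a second stopping condition of less than 1% of the dose recovered in urine/faeces over 24 hours.

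Section 11.2 also lists "Apparent plasma clearance (CL/F), for AZD8931 only", without stating which dose is used. Section 12.1.2 restricts the PK analysis set to subjects "without important protocol deviations or violations thought to significantly affect the PK of the investigational product". Vomiting is not named there.

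**The concern.** Excretion is part of the primary objective (Section 2.1), and Section 1.3 calls this a mass balance study. Section 3.2 sets the collection period so that almost no label is left to be excreted. The rest of the plan serves that aim: urine and faeces are collected to 240 hours, toilet paper for 48 hours, and two rinses of the dosing vessel are swallowed. A 2-hour limit on vomit does not fit it.

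Two gaps follow. Vomit within 2 hours is measured, but no listed variable or matrix receives the result. Vomit after 2 hours need not be kept, so any label in it is never measured. In either case low recovery in urine plus faeces could be misread as label retained in the body, when it had left by a third route. With 6 subjects, one such case is visible in the summary.

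**Working it through.** **The dose, which is the denominator (Section 5.5.1).** 80 mL × 2 mg/mL = 160 mg AZD8931. 160 × 1.489 = 238.24 mg of the salt, which agrees with 0.2978% w/v in 80 mL. 238.24 mg × 0.84 µCi/mg = 200.1 µCi, against 200 µCi stated. 200 × 0.037 = 7.4 MBq. The stated dose reproduces.

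**Assumptions.** Let v be the fraction of the dose lost in vomit. The documents give no figure, so v = 10%, 20% and 40% are used. Let R be the recovery of the retained dose in urine plus faeces; R = 100% gives the ceiling. One subject of 6 vomits (Section 12.3), or one of the minimum of 4 evaluable (Section 5.2).

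**Recovery.** In the affected subject fe_u+f = R(1 − v). At R = 100% the mean falls by v/6 or v/4.

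**CL/F.** CL/F = Dose/AUC. If exposure falls in proportion to the dose lost and the nominal 160 mg is used, CL/F is multiplied by 1/(1 − v). The geometric mean of 6 is multiplied by (1/(1 − v))^(1/6). Proportionality is reasonable here: Section 3.2 reports it from 40 to 160 mg, and a 40% loss leaves 160 × 0.6 = 96 mg.

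| v (assumed) | Maximum fe_u+f | Fall in mean of 6 (points) | Fall in mean of 4 (points) | CL/F, that subject | CL/F, geometric mean of 6 |
|---|---|---|---|---|---|
| 10% | 90% | 1.7 | 2.5 | × 1.11 | × 1.02 |
| 20% | 80% | 3.3 | 5.0 | × 1.25 | × 1.04 |
| 40% | 60% | 6.7 | 10.0 | × 1.67 | × 1.09 |

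If the vomited label would not have been absorbed anyway, AUC is unaffected and the CL/F columns do not apply. The recovery columns still do.

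**The 90% level in note c.** If it is judged on urine and faeces alone, it is out of reach once v exceeds 1 − 0.90/R: 10% at R = 100%, or 5.3% at R = 95%.

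**With vomit counted.** Total recovery is R(1 − v) + v. At R = 100% this is 100% for every v. At R = 95% and v = 20% it is 76% + 20% = 96%. Using the dose net of the measured loss returns the CL/F factor to 1.

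**The case against.** A reader might infer that a subject who vomits will necessarily be reported with incomplete excretion and inflated clearance. The documents do not support that. Vomit within 2 hours is counted, so that loss is known. Section 11.2 speaks of a percentage of dose and does not say that CL/F uses 160 mg whatever is lost. It also allows further PK parameters where appropriate, and Section 12.1.2 has the study team agree how to treat data affected by deviations. Which dose enters CL/F, and whether the subject is summarised, are details that an analysis plan not shown here may settle.

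Nor does vomiting have to make the 90% level unreachable. Note c contrasts total recovery with recovery in urine/faeces, so its total can be read to include vomit. The rule is permissive, and the condition of less than 1% in 24 hours can still end collection.

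The likelihood is also uncertain. Section 1.1 names gastrointestinal toxicity as dose limiting, but in animals. Sections 1.4 and 3.2 describe single doses up to 200 mg as well tolerated in healthy men, and the adverse events described from the 160 mg food-effect study are mainly of the skin.

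All of this stands and narrows the point. It does not remove the collection gap: no later analysis can recover label in vomit that was discarded. Nor does it change the fact that the protocol orders a measurement and gives it no destination.

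**Conclusion.** The point holds as a cheap improvement to the collection rule and the list of recovery variables. Vomit after 2 hours need not be kept, and vomit that is measured enters no listed variable or matrix. Unless corrected, one affected subject has a ceiling on fe_u+f of 90%, 80% or 60%, and lowers the mean of 6 by 1.7, 3.3 or 6.7 points, for assumed losses of 10%, 20% or 40%. CL/F on the nominal dose would be overstated by 11%, 25% or 67% in that subject, but only by about 2%, 4% or 9% in the geometric mean of 6.

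These figures rest on assumed losses, R = 100%, one affected subject and, for CL/F, a proportionate loss of exposure and an uncorrected dose. The effect is zero if nobody vomits, and the documents give neither a vomiting rate nor a likely size for loss after 2 hours. Early loss can be corrected from the measured counts; late loss cannot. The handling of CL/F and of the PK analysis set can be left to the study team or the analysis plan.

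**What to change.** - In Section 3.1, retain and count all vomit produced during the residential collection period, not only that of the first 2 hours.
- In the Synopsis and Section 11.2, add the amount of radioactivity in vomit (Ae_v) and its percentage of dose (fe_v), and a total recovery of urine, faeces and vomit as a percentage of dose. Name vomit in the listings and matrices of Section 12.2.3 and in the laboratory scope of Section 6.4.2.
- State in Table 1 note c that total recovery means this three-part sum.
- Do not drop a subject's PK parameters automatically for any measurable radioactivity in vomit. A 0.5% loss changes CL/F by about 0.5% (1/0.995), which does not justify losing one of 6 subjects. Report the parameters beside the measured loss, and have the study team decide on summarising them before database lock.

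The cost is wording in the protocol and laboratory manual, plus a few extra counts only if vomiting occurs.
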